3 STUDY ENDPOINTS

- Primary 1: Subjective questionnaires of product evaluation (Duke Sensory Scale, Product Evaluation Scale, Drug Effects, Hedonic Attribute), withdrawal (MNWS, QSU-B, PANAS), and readiness to quit (contemplation ladder).
- Primary 2: Number of cigarettes smoked per week during the field period.
- Secondary: Awareness and beliefs about filter ventilation and perceptions of messaging.
- Secondary: Exhaled CO is defined as level of CO measured in exhaled breath after a 15 s breathhold. This is typically 10ppm or above in daily smokers and <3 ppm in nonsmokers.
- Secondary: Smoking topography as assessed by particulate matter retained on used filters.

Roswell Park Protocol Number: I 757820

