5 STUDY TIMELINES

5.1 Duration of an Individual Subject's Participation in the Study

The proposed study consists of multiple videoconferencing sessions (a total of 3) throughout a 2-week field study. Following informed consent, participants will be randomly assigned to 1 of 4 message conditions and use the assigned product for 2 weeks. This 2-week field study involves participants logging their use of tobacco products, while the weekly videoconferencing sessions involve additional questionnaires and guidance about field data collection.

Roswell Park Protocol Number: I 757820

	Data Collection Sessions (Weekly)			Field (Daily for 14 days)
	Video 1	Video 2	Video 3	Ecological Momentary Assessment
Tobacco Use Behavior				
Cigarettes per Day	X	X	X	X
Other Tobacco Use	X	X	X	X
Context of Use (e.g., location)				X
Questionnaires				
Message Perceptions (response, health risk, purchase)	X All messages	X Randomly Assigned Message	X Randomly Assigned Message	
Vent Awareness	X	X	X	
Product Evaluation (Duke Sensory, Product Evaluation Scale, Drug Effects, Hedonic Attribute)	X	X	X	X Select Items
Readiness to Quit (Contemplation Ladder)	X	X	X	
Withdrawal (MNWS, QSU-B, PANAS)				X Select Items
Attention to Messaging				X
Biomarkers				
Exhaled CO				X
Topography via Filter Analysis				X

Estimated date for the investigators to complete this study

Data collection should be completed by 12/31/2022.

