11.2 Treatment

This study will use two types of cigarettes. One set of cigarettes are commercially available Marlboro cigarettes (Philip Morris USA, Richmond, VA), all combustible King size (83mm) cigarettes consisting of filler, filter paper, tipping paper, cigarette paper, tipping glue and seam glue. Specific varieties are listed in the table. Products will be sourced at retail from local outlets.

Alternatively, participants may receive investigational “roll your own” (RYO) cigarettes that will be prepared in the laboratory. These cigarettes will be made to match the commercially available Marlboro cigarettes. These cigarettes will be prepared with conventional tobacco (e.g., Good Stuff) rolled using an automatic rolling machine (e.g., Powermatic III+) and packaged into 20 rod packs. The investigational RYO cigarettes will use ventilated filter tubes (e.g., ~25-37% filter ventilation). The dose of nicotine in these RYO cigarettes will be similar to conventional cigarettes.

Within each pair of products is a nonmenthol and menthol equivalent. Participants who report regularly smoking menthol cigarettes will receive the menthol versions for the study.

Variety	Vent %	Filter length (mm)	Tobacco weight (mg)
Special Blend Smooth Mellow	30.6	27	625.1
Smooth Fresh Menthol	37.6	27	630.8

Additionally, cigarettes will be paired with messaging about filter ventilation. This message will be affixed to the front exterior of each package provided to participants.

- No Message (e.g., unaltered cigarette pack).
- Neutral Message: “Nothing about this product’s color or name means that it will protect a smoker from the health risks of smoking.”
- Compensation Message: “This product has a ventilated filter. Filter vents increase how deeply a smoker inhales without them knowing, which can increase the health risks of smoking.”
- Blocking Message: “This product has a ventilated filter. Be sure not to block the vent holes with your fingers or lips, which can increase the health risks of smoking.”

Roswell Park Protocol Number: I 757820

With these conditions, ‘no message’ serves as a true control (smoking as normal), while the neutral message serves as a control message to determine if added messaging impacts behavior/perceptions, even if that message is not informational. The compensation and blocking messages will determine if added messaging about the health risks of filter ventilation affect behavior/perceptions, and which type of message has the greater impact.

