In the event of REDCap being inaccessible for a study visit, .pdf files or paper copies of the consent will be provided to the participants and the participants will be able to sign and return or submit a photo of the signed copy.

The participant will then be randomized to 1 of 4 message conditions (No message, Neutral message, Compensation message, Blocking message) and arrangements will be made to mail, deliver, or have participants pick up study materials (study cigarettes with pack messages, CO

Roswell Park Protocol Number: I 757820

monitor, scales, butt collection materials, shipping materials, etc.). Participants will be provided with two weeks of materials.

Session 1. Session 1 will occur upon receipt of study materials by the participant. Participants will complete a baseline intake questionnaire including smoking and tobacco use history, nicotine dependence scales, SCQ, TRIRISK, delay discounting, respiratory symptoms, and knowledge, attitudes, and beliefs about filter vents. In addition, participants complete questionnaires on message perceptions (response to messaging, health risk, purchase intention) for all pack messages. Questionnaires also will be used to get baseline assessments of the user's usual brand of cigarettes (Duke Sensory Scale, Product Evaluation Scale, Hedonic Attribute Scale). Participants will be instructed to record each smoking event using the EMA app provided (described in more detail below) and to retain all spent cigarette butts and unused product. Participants will be informed that they are free to use other tobacco products (though they will not be provided as part of the study), and that these should be recorded using EMA. Participants will be provided for cigarettes for a total of two weeks, with the amount determined by normal self-reported weekly consumption rounded to nearest whole pack.

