Remote Data Collection. Participants will complete the two-week study remotely using EMA methods. At the conclusion of Session 1, participants will be trained to record their assigned product use via EMA for data collection. Specifically, participants will respond to 5 scheduled questionnaires daily. These questionnaires are designed to assess product consumption, context of use (e.g., location, social situation), and subjective responses (e.g., withdrawal, product evaluation, message attention - more details on surveys provided below). Participants will be prompted to measure their exhaled-air CO level and product weight twice each day using a personal monitor provided to them. Participants will also retain all spent cigarette butts and unused products throughout the two weeks.

Day 3 Check-in: Research assistants will monitor EMA data to ensure the participant is compliant with study procedures. Participants will send a secure text message (via Twilio) or arrange a phone call to discuss the participant's compliance in the initial days of data collection. Participants that are not responding to prompts will be retrained to ensure they understand procedures and warned that compliance must increase to continue participating in the study.

Session 2 will take place one week later (\pm 2 days) via remote videoconference using an institution-approved software with a password protected meeting (e.g., WebEx, Microsoft Teams, Zoom). The Session 2 videoconference will include the completion of questionnaires on vent awareness, product evaluation, and readiness to quit (similar to Visit 1). Participants will again be asked on message perceptions, but only in relation to their randomly assigned condition.

Session 3 will take place one week later (\pm 2 days) via remote videoconference. The same questionnaires from Session 2 will be administered again. Laboratory staff will guide participants to place all materials (retained filter butts, unused products, unsigned payment receipts) in the provided shipping box. Arrangements will be made for the participant to return materials or for research staff to pick up materials. Participants will be paid for Visit 3 upon verification of returned study materials.

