1. Do you have any children living in your home? Yes, No

If yes, How many? Ages?

Smoke Free home and vehicle policies

These next few questions ask about rules of using tobacco inside your home. Please think about everyone who might be in your home including children, adults, visitors, guests, or workers. For tobacco products that are burned, such as cigarettes, cigars, pipes, or hookah, which statement best describes the rules about smoking a tobacco product inside your home?

1 It is not allowed anywhere or at any time inside my home

2 It is allowed in some places or at some times inside my home

3 It is allowed anywhere and at any time inside my home

-8 DON'T KNOW

-7 REFUSED

Do you have a car (this includes a car, van, suv, or any other enclosed vehicle)?

IF YES: For tobacco products that are burned, such as cigarettes, cigars, pipes or hookah, which statement best describes the rules about smoking a tobacco product inside your car?

1 It is not allowed anywhere or at any time inside my car

2 It is allowed in some places or at sometimes inside my car

3 It is allowed anywhere and at any time inside my car

-8 DON'T KNOW

-7 REFUSED

Vape-free home and vehicle policies

For electronic cigarette products, such as e-cigarettes, vape pens, tanks, mods, JUUL, which statement best describes the rules about vaping inside your home?

1 It is not allowed anywhere or at any time inside my home

2 It is allowed in some places or at sometimes inside my home

3 It is allowed anywhere and at any time inside my home

-8 DON'T KNOW

-7 REFUSED

IF CAR=YES: For electronic cigarette products, such as e-cigarettes, vape pens, tanks, mods, JUUL, which statement best describes the rules about vaping inside your car?

Roswell Park Protocol Number: I 757820

- 1 It is not allowed anywhere or at any time inside my car
- 2 It is allowed in some places or at some times inside my car
- 3 It is allowed anywhere and at any time inside my car
- 8 DON'T KNOW
- 7 REFUSED

Responses to pack messaging

In your opinion, how would you rate the label you just saw on each of the following characteristics

1='Not at all' to 10='Extremely'.

Effective in discouraging smoking in youth
Effective in encouraging smokers to quit
Believable information
Truthful information
Exaggerated information
New information
Hard to understand
Applies to me

Message Perceptions

This message is:
Worth remembering
Grabs attention
Powerful
Informative
Meaningful
Convincing

Effect Perceptions

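### Every arm reads and rates all pack messages at Session 1, so the no-message arm is not the stated true control and the awareness and belief contrasts measure a label on top of one shared viewing

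*Combined protocol and SAP*

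**What the plan says.** Section 11.3 sets the sequence. After consent, "The participant will then be randomized to 1 of 4 message conditions" and the study materials, including packs carrying the assigned message, are sent out or collected. "Session 1 will occur upon receipt of study materials by the participant". In that session "participants complete questionnaires on message perceptions (response to messaging, health risk, purchase intention) for all pack messages". Training on field procedures follows, and then the two field weeks begin.

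The Section 5.1 table agrees: the message-perception row reads "X All messages" at Video 1 and the randomly assigned message at Videos 2 and 3. For Session 2, Section 11.3 says "Participants will again be asked on message perceptions, but only in relation to their randomly assigned condition", and Session 3 repeats the Session 2 questionnaires. The rating form in Appendix C asks "how would you rate the label you just saw on each of the following characteristics", so a message has to be shown before it can be rated.

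Section 11.2 says the no-message condition "serves as a true control (smoking as normal"), and sets the trial the task of finding which type of vent message has more impact. Section 3 lists "Secondary: Awareness and beliefs about filter ventilation and perceptions of messaging". Section 1.2 opens with the hypothesis that exposure to the messages raises awareness and knowledge. Section 22.1 compares the four conditions and does not mention a viewing common to all of them.

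**The concern.** The control arm is meant to show what happens without messages. As scheduled, it has read every message immediately before follow-up starts. The compensation and blocking arms have likewise each read the other's text, which bears on the comparison of message types.

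A single reading is likeliest to move knowledge, and knowledge carries the first stated hypothesis. If controls learn at Session 1 part of what the labels would teach, the difference at Sessions 2 and 3 is smaller than the difference between exposed and unexposed smokers. A null result would then have two explanations, that the labels do not inform or that the controls were informed as well. The planned analysis cannot tell them apart.

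**Working it through.** **Step 1. Exposure by arm, from Sections 5.1, 11.2 and 11.3.**

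| Arm | Session 1 | Field weeks | Sessions 2–3 ratings |
|---|---|---|---|
| No message | all messages | unaltered pack | assigned condition only |
| Neutral | all messages | neutral label | assigned condition only |
| Compensation | all messages | compensation label | assigned condition only |
| Blocking | all messages | blocking label | assigned condition only |

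The arms differ only in the pack used in the field weeks and in the follow-up ratings tied to it. The contrast is therefore label versus no label, given one viewing of everything.

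**Step 2. What the viewing conveys, against what the vent items ask (Section 11.2; Appendix C).** Both vent messages say that the product has a ventilated filter. One adds that vents deepen inhalation, the other that blocking the holes can raise health risk.

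- Item 2 (ever seen or heard of the holes): the viewing bears on it directly. The questionnaire itself also tells every arm about the holes, at every session.
- Items 5–7 (effect of blocking on taste, tar and nicotine): neither message gives these answers. Carry-over would be inference by the participant.

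**Step 3. Size.** The plan gives no target difference or power for the vent items, so there is no figure of its own to reproduce. Its sample size does reproduce: 300 × 0.80 = 240 completers, and 240/4 = 60 per arm if allocation is equal (the ratio is not stated).

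The following is an illustration only. Let p0 be awareness before exposure, p1 the level in the label arm, and c the share of the label effect that one viewing already conveys. The control level becomes pc = p0 + c(p1 − p0). Power for a two-sided two-proportion z-test is

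Φ{[(p1 − pc) − z(1−α/2)·√(2p̄(1−p̄)/n)] / √[(pc(1−pc) + p1(1−p1))/n]}, with p̄ = (pc + p1)/2.

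Section 2.2 gives p0 = 44.7%. With n = 60, 80% power needs p1 = 69.8% at α = 0.05, or 75.5% at α = 0.008. The plan does not say whether 0.008 applies to these items, so both are shown.

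Example, α = 0.05, c = 0.25: pc = 0.447 + 0.25 × 0.2506 = 0.510; difference 0.188; p̄ = 0.604; [0.188 − 1.96 × 0.0893]/0.0876 = 0.147; power 56%.

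| Label effect | α | c = 0.10 | c = 0.25 | c = 0.50 |
|---|---|---|---|---|
| 80%-power threshold | 0.05 | 71% | 56% | 30% |
| 80%-power threshold | 0.008 | 69% | 50% | 20% |
| Label arm reaches 90% | 0.05 | >99% | 99% | 87% |
| Label arm reaches 90% | 0.008 | 99% | 95% | 65% |

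Three limits apply.

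- c is assumed throughout. If the effects of viewing and label simply add on the linear scale, there is no loss.
- The anchor is uncertain. Section 2.2 also reports 1079 aware respondents out of 1986, which is 54.3%. From that anchor, the 90% rows at c = 0.50 become 71% and 44%.
- The threshold rows are close to generic. Halving almost any effect that has 80% power at 0.05 leaves about 30% power (31% from the 54.3% anchor).

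**Step 4. Timing of any moved rating (Section 11.3).** Sessions 2 and 3 each fall one week after the session before, within 2 days. Session 3 can therefore come at (7 − 2) + (7 − 2) = day 10, with EMA days still to run.

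**The case against.** The control label in Section 11.2 can be read as describing pack conditions only, since the aims concern messages on packs. On that reading, label versus no label is exactly the intended contrast. Rating all messages also looks deliberate: the schedule separates it from the assigned-message rating, and perceptions of messaging belong to the same secondary endpoint. Sections 11.3 and Appendix D list the vent items ahead of the message ratings. The item most open to the viewing is one the questionnaire already prompts in every arm, and the remaining belief items are not answered by the messages.

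Much of this stands. The contrast is valid, the rating has a purpose, and the effect on items 5–7 is conjecture. Two things remain. Smoking as normal does not describe people who have just read and rated warnings about vents, and nothing in the plan defines the contrast as incremental. The listed order is not stated as a rule, and it would protect only the baseline, because the Session 2 and 3 outcomes follow the viewing in any case.

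A reader might go further and infer that the randomised comparison is biased, that the trial is underpowered for awareness, or that the primary endpoints are compromised. The documents support none of these. The viewing is common to all arms, no target effect or value of c is given, and nothing shows that one viewing changes cigarette counts or product ratings.

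**Conclusion.** The concern holds as a mismatch between the stated control and the procedures, confined to the meaning of the awareness and belief contrasts. Those contrasts estimate the effect of two weeks with an assigned label after one viewing of all messages. Attenuation is plausible for vent awareness and speculative for items 5–7. It could range from none to substantial depending on c, which the documents do not give, so the power figures show sensitivity and are not estimates. They also assume 60 completers per arm and a binary item. The consent form is not in the text available, so what it discloses about vents is unknown. This should be fixed because the remedy is cheap and a null on the first hypothesis would otherwise be easy to misread. It does not threaten the validity of the trial.

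**What to change.** 1. **Sections 5.1 and 11.3:** state as a fixed order that the baseline vent items are completed before any message is shown. Labelled packs will already have arrived, so this protects the baseline only in part. It costs one sentence and a form order.

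2. **Choose one of two options.**
   - (a) Show no unassigned message at Video 1; the no-message arm rates none. Collect ratings of unassigned messages after both the last outcome questionnaire and the last EMA report. Placing them in Session 3 is not sufficient, given Step 4. This needs a schedule amendment and re-ordered REDCap forms, and Session 1 content would differ by arm. It gives up the pre-field within-person comparison of messages, because later ratings follow two weeks with one label.
   - (b) Keep the all-message rating, replace the control description in Section 11.2, and define the Section 22.1 contrasts as assigned label versus no label after one viewing of all messages. State that a null on awareness or beliefs will not be read as evidence that the messages do not inform. This costs wording only.

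3. **Section 22.1:** report the Video 1 to Video 2 change in vent items in the no-message arm as a descriptive flag for shared exposure, noting that it cannot separate message viewing from reactivity to the questionnaire.

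Neither option gives a fully naive control. The vent questionnaire goes to every arm, the letter to prior participants mentions filter ventilation, and the EMA items about the warning label carry no printed restriction by arm.

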11.4 Data To Be Collected

- **Baseline measures and covariates will assess:**
 - Demographics (age, sex, race/ethnicity, education, income)

Roswell Park Protocol Number: I 757820

- Tobacco use behaviors (consumption, brand, menthol preference, past quit attempts)
- Delay discounting
- A series of previously used items will assess knowledge and perceptions of filter vents.^{113,117}
- Nicotine dependence will be assessed using:
 - Fagerström Test for Nicotine Dependence (FTND¹¹⁸)
 - PROMIS

Behavioral aspects of cigarette dependence will be assessed using:

- The Glover-Nilsson scale^{120,121}
- The different scales are used to capture different dimensions of tobacco dependence.¹²²
- Exhaled air CO will be collected by the participants twice each day using a personal CO monitor provided by the researchers. The CO monitors provided are coVita iCo™ Smokerlyzers®, which are intended for research and consumer use and are compatible with a Smartphone or tablet (iOS or Android).

Perceptions of product messaging: In this study, we are interested in risk perceptions, smoking-related expectancies, and behavioral intentions. We will assess risk perceptions for specific products using a risk ladder.¹²⁹ More generalized perceptions of risk for cancer are captured using the tripartite risk (TRIRISK) measure, which captures deliberative, affective, and experiential components of risk perception.¹³⁰ The adult smoking consequences questionnaire (SCQ) will assess smoking-related expectancies.^{103,131} Behavioral intention is assessed using Juster's consumer purchase probability scale, a widely used marketing metric.¹³²⁻¹³⁴ Additional questions will include responses to messaging (e.g., message was powerful, memorable).

Responses to product use will be assessed in a number of ways: Response to nicotine dose will be assessed using the Minnesota Nicotine Withdrawal Scale (symptoms of nicotine withdrawal).¹³⁵ Cigarette craving in field will be assessed using the Brief QSU commonly used in cue reactivity research. Behavioral economic measures will assess product demand. A delay discounting task will assess preference for immediate reward,¹⁴⁸ while purchase tasks will be used to estimate level and elasticity of demand.¹⁴⁹⁻¹⁵¹ Sensory measures will be collected using the Duke Sensory Scale and Hedonic Attribute Scale. Drug effect measures include the Product Evaluation Scale and Drug Effects/Liking Scale.

Cigarette tracking via EMA: For the field study, the key outcome is the total number of cigarettes smoked. Participants will be asked to complete REDCap questionnaires on their personal phone (iOS or Android). Participants can use the MyCap application to respond to questionnaires. Additionally, REDCap can interface with Twilio, a secure text-messaging platform, to send study related messages and surveys via SMS (text messaging). Proposed EMA methods are based on established best practices. Participants will complete 5 questionnaires every day. These questionnaires will occur at the same time each day: 11am, 1:30pm, 4pm, 6:30pm, and 9pm. These daily reports will be used to assess cigarette and e-cigarette consumption, and 10 items relating to subjective ratings of nicotine withdrawal (e.g., craving, irritability) and mood (e.g., calm/relax, happy). At 11am only, participants will complete selected items from the Hedonic Attribute Profile and Product Evaluation Scale. At 9pm only, participants will be asked to rate the taste, satisfaction,

Roswell Park Protocol Number: I 757820

enjoyment, and craving relief from the cigarettes they smoked that day. Participants will also be asked to take a CO measurement at this time. At the 1:30 and 6:30 prompts, participants will be asked about situational factors related to use (Location, smoking permitted, with others, activity, craving) and complete the Duke Sensory Evaluation scale. Participants also will be asked to take a picture of their research cigarette pack to ensure compliance. Surveys will be open for 1 hour after the scheduled time for completion. Appendix C demonstrates the EMA schedule and the questions asked at each daily report and pseudo-random prompt. Participants can earn up to \$10 for each day of EMA compliance, with compliance being defined as responding to ≥ 4 of 5 daily prompts (up to 14 days, totaling \$140). Studies that used similar methods had $>90\%$ compliance. [189, 190].

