This message:
Discourages me wanting to smoke
Makes smoking seem unpleasant to me
Makes me concerned about health effects of smoking

Negative Affect

How much did the label make you feel:
Anxious
Sad
Scared
Guilty
Disgusted

Roswell Park Protocol Number: I 757820

Thinking of Harms

How much did the labels make you think about:
The chemicals in the smoke of the cigarettes
Health problems caused by smoking
The harm your smoking might be doing to you
The harm your smoking might be doing to other people

Would you support or oppose a policy that required this label to appear on cigarette packages?
Strongly oppose – Strongly support

Would you support or oppose a policy that required this label to appear in advertising for cigarettes?
Strongly oppose – Strongly support

Remote Data Collection – EMA Schedule and Questionnaires

3 Daily Reports – 11 am, 4pm, 9pm (assessments < 5min)

How many cigarettes have you smoked since the last prompt?

How many of these cigarettes were research cigarettes?

How many of these cigarettes were not research cigarettes?

How you used any other tobacco products since the last prompt?

If yes: What product? How many times did you use it?

Please record your product weight with the provided scale.

RIGHT NOW: How would you rate your (0 – 100 VAS):

- Craving
- Irritability
- Anxiousness/nervousness
- Difficulty Concentrating
- Stress
- Bored
- Calm/Relaxed
- Happy
- Alert
- Enthusiastic

Provide Reminder to collect all cigarette butts in provided materials, store used pods

11 am Only (additional questions)

Hedonic Attribute Profile: In the past day, how would you rate the research cigarettes (1-7 Likert)

Draw

Irritation

Smoothness

Roswell Park Protocol Number: I 757820

Strength

Tobacco Taste

Similarity to Usual Brand

Product Evaluation Scale (1 - 7 Likert):

Was it satisfying?

Did it taste good?

Did it calm you down?

Did you enjoy the sensations in your mouth?

Did it reduce your craving for a cigarette?

Were there bothersome side effects?

Did you enjoy using the product?

Would you be willing to use the product long term?

Record CO measurement

9pm Only (additional questions):

Record CO measurement

Reflect on today as a whole: How would you rate your (0 – 100 VAS)

- Craving
- Irritability
- Anxiousness/nervousness
- Difficulty Concentrating
- Stress
- Bored
- Calm/Relaxed
- Happy
- Alert
- Enthusiastic

Thinking of the cigarettes you smoked today: How would you rate (0 – 100 VAS)

- Tastes like my own brand

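### The cigarette-count primary outcome rests on participants' own reports alone; the returned cigarettes and butts should be counted as a prespecified supportive check

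*Combined protocol and SAP*

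**What the plan says.** Section 3 lists "Primary 2: Number of cigarettes smoked per week during the field period" without naming the source of the count. Section 11.4 supplies it under the EMA heading: "For the field study, the key outcome is the total number of cigarettes smoked". The item in Appendix C (EMA schedule) is "How many cigarettes have you smoked since the last prompt", followed by a split into research cigarettes and others, the second part being "How many of these cigarettes were not research cigarettes". Section 11.4 adds: "Surveys will be open for 1 hour after the scheduled time for completion". The table in section 5.1 also lists cigarettes per day at the three video sessions, with no source other than the participant.

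On materials, section 11.3 sets each participant's two-week supply "with the amount determined by normal self-reported weekly consumption rounded to nearest whole pack", so the number issued is known. It continues: "Participants will also retain all spent cigarette butts and unused products throughout the two weeks". At Session 3 staff guide the packing of butts and unused product, and "Participants will be paid for Visit 3 upon verification of returned study materials".

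The stated uses of the butts are topography (section 3) and vent blocking or mouth-level exposure (section 11.1). Unused product has no stated analytic use. Section 22.1 names neither a count of returned items nor a reconciliation with EMA.

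**The concern.** The outcome is a self-report by people who can see their allocation. Three arms carry a label. The compensation and blocking labels link vents, or blocking them, to higher health risks, and the neutral label also mentions the health risks of smoking. Seeing such a label on every pack for two weeks could change what a participant is willing to report as well as what they smoke. Randomisation does not remove that kind of error.

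Sections 1.2 and 11.1 predict no change in smoking behaviour. If a labelled arm nevertheless reported fewer cigarettes, the plan has no second count to help tell a real fall from a change in reporting. The items needed for one are already coming back to the sites. If they are not counted on return, the check may be impossible later.

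**Working it through.** **Inputs.** Section 22.1 gives a difference of 3.9 cigarettes per day (CPD), described as 25%; SD 7.6; 240 participants at the end of the field study; and a pairwise alpha of 0.008. Section 11.3 gives four arms. The allocation ratio is not stated, so equal arms of 240/4 = 60 are assumed. The documents give no figure for reporting error, so a range is assumed.

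**The plan's own figure.** SE = 7.6 × √(2/60) = 1.388. The two-sided critical value at 0.008 is 2.652. Power for 3.9 CPD is about Φ(3.9/1.388 − 2.652) = Φ(0.159) = 56.3%, against the stated 80%. At an uncorrected 0.05 it is 80.3%. This mismatch is a separate matter. It does not decide the present point, but the same inputs are used below.

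**Implied reference level.** 3.9/0.25 = 15.6 CPD.

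**Effect of a reporting differential.** Suppose the true difference is zero and one arm of a pair under-reports by an extra share u of 15.6 CPD, with the SD unchanged. The spurious difference is b = u × 15.6. The chance of a significant result is 1 − Φ(2.652 − b/1.388) + Φ(−2.652 − b/1.388).

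| Assumed u | b (CPD) | b as share of 3.9 | False positives per pair |
|---|---|---|---|
| 0 | 0 | 0 | 0.8% |
| 5% | 0.78 | 20% | 1.9% |
| 10% | 1.56 | 40% | 6.3% |
| 15% | 2.34 | 60% | 16.7% |

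A noncentral t calculation at 0.05/6 gives the same 1.9% and 6.3% for the 5% and 10% rows.

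**What a return count would have to pick up.** Over 14 days, 0.78 CPD is 0.78 × 14 = 10.9 cigarettes and 1.56 CPD is 21.8. At 20 per pack that is about half a pack or one pack per participant. Loss or sharing on that scale would blur the comparison.

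**The ceiling.** At 15.6 CPD, usual use over 14 days is 218.4 cigarettes, or 10.92 packs. Rounded to 11 packs, the supply is 220. If rounding is applied weekly, 109.2 cigarettes is 5.46 packs, rounded to 5, and the two-week supply is 200. Either way the count cannot rise much above usual consumption, and in the second case it cannot reach it.

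**The case against.** Several points on the other side stand.

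- A reader might infer that the labelled arms receive risk information that the no-message arm never sees. The documents do not support that. Sections 5.1 and 11.3 have every participant rate all pack messages at Session 1, before EMA begins. The arms differ in repeated pack exposure only.
- A reader might infer that the labels tell participants that smoking itself raises their risk. No label says so. Two concern vents or vent blocking, and the neutral label mentions health risks without saying that they are raised.
- The neutral arm controls for the presence of a label. If the mechanism is label against no label, it bears on three of the six pairs. Compensation and blocking against neutral are largely protected.
- Exhaled CO, recorded within EMA, could diverge from reported counts and give a signal. It is imperfect, because inhalation may change too, and the plan does not link it to Primary 2.
- A reader might take issued minus returned as an objective replacement for EMA. It is not. Participants control what comes back. A shift to own-brand cigarettes lowers the count without less smoking, and only self-report corrects for that. Materials come back once, so there is no weekly split, and section 12.2 describes no return from withdrawn participants.
- A gap between EMA and returns also arises from missed one-hour windows, so it is not a pure measure of misreporting.

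What remains is that no section counts the returns or compares them with EMA.

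**Conclusion.** The point holds as a low-cost improvement. Primary 2 depends on unblinded self-report, and a second, largely independent source for research cigarettes is collected but not used for counting. Differential reporting is plausible, mainly in contrasts with the no-message arm, but neither its presence nor its direction is shown.

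The rates of 1.9% and 6.3% are illustrations. They rest on assumed differentials of 5% and 10%, equal arms of 60, SD 7.6, a simple two-group comparison and no true effect. They do not estimate bias in this trial, and they do not apply to all six pairs. The documents do not support concluding that EMA is an invalid primary measure or that it should be replaced.

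**What to change.** 1. State in section 3 and section 22.1 that Primary 2 is taken from the EMA reports.
2. At the existing verification of returned materials, record for each participant the number of research cigarettes issued, returned unused, and returned as butts.
3. Prespecify a supportive two-week analysis by arm of research cigarettes used, defined as issued minus returned unused and cross-checked against butts. Present it alone and with EMA-reported non-research cigarettes added.
4. Report by arm the difference between this count and the EMA research-cigarette total, next to the prompt-completion rate by arm, because missed prompts also create a difference.
5. Keep EMA for daily and weekly timing.
6. State the limits: the count is capped by a supply set at usual consumption; own-brand use lowers it and is corrected only by self-report; loss, sharing or discarding adds error; a single return gives no weekly split; and no return is described for withdrawn participants.

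The cost is some counting time and a paragraph in the statistical plan. No visit, participant task or sample size changes.
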